5.4. Creatinine Clearance

Creatinine clearance will be calculated using the Cockcroft-Gault Equation. If the calculated creatinine clearance is <60 mL/min, PrEP will be halted temporarily and creatinine testing repeated within two weeks. If renal function returns to normal ($\text{CrCL} \geq 60$ mL/min), PrEP may be re-started.

5.5. Toxicity Management

The site investigator has the discretion to interrupt FTC/TDF at any time if s/he feels that continued medication use would be harmful to the participant or would interfere with treatment deemed clinically necessary according to the judgment of the investigator. Clinical or laboratory abnormalities that require follow-up will be documented, and the participant will be contacted to schedule an interim visit for follow-up and/or repeat laboratory testing if indicated. All participants reporting an adverse event (AE) Grade 3 or higher or any grade for creatinine will be followed clinically until the occurrence resolves (returns to baseline grade, defined as grade at Enrollment) or stabilizes. PrEP will be discontinued if the CrCl decreases below 60 ml/min and serum creatinine will be monitored. SAEs designated to be related to PrEP will result in temporary hold of PrEP. In the case of temporary holds, the hold will continue until the event is stabilized or resolved. In such cases, PrEP may be reinitiated at the discretion of the Investigator.

5.6. Social Impact Reporting

It is possible that participants' involvement in the study could become known to others, and that a social impact may result (i.e., because participants could be perceived as being HIV-infected or at "high risk" for HIV infection). For example, participants could be treated unfairly, or could have problems being accepted by their families and/or communities. These are social harm events. Social harm events are those negative events that a participant reports as affecting them as a result of being involved in a research study. A social harm that is reported by the participant and judged by the study staff to be serious or unexpected will be reported to the site's IRBs at least annually, or according to local requirements.

In the event that a participant reports a social harm, every effort will be made by study staff to provide appropriate care and counseling to the participant as necessary, and/or referral to appropriate resources for the safety of the participant. While maintaining participant confidentiality, the site may engage the Youth Community Advisory Board (YCAB) in exploring the social context surrounding instances of social impacts, to minimize the potential occurrence of such an impact.

6.0 STATISTICAL CONSIDERATIONS

6.1. Review of Study Design

SMART design to evaluate response to scalable adherence strategies. At enrollment, women will be randomized to either the SOC adherence support plus WhatsApp groups, to provide social support, or SOC adherence support plus weekly two-way SMS messages, to triage and provide additional counseling to manage side effects, adherence issues, or any other concerns. All participants will attend monthly visits for the first 3 months of follow-up and will receive periodic one-way reminder SMS messages about upcoming clinic appointments. In both groups, intracellular tenofovir drug levels based on DBS collected at 2 months will be used as an objective measure of adherence. At the Month 3 visit, women who are classified as "responders" (those with high adherence, based on a TFV-DP threshold of 500 fmol/punch measured at the Month 2 visit) will continue with the SOC counseling and their initial randomization of either two-way SMS or WhatsApp groups but they will be switched to a quarterly visit schedule. Non-responders (those with low adherence based on the Month 2 visit drug levels) will be randomized to more intensive adherence support – monthly visits for SOC adherence and special issue counseling or quarterly visits with drug level feedback at 3 and 6 months in addition to their initial randomization arm intervention (two-way SMS or WhatsApp and one-way reminder SMS messages). Follow-up visits will occur for all participants monthly until Month 3 and then quarterly for 9 months for responders and non-responders randomized to drug level feedback. Non-responders who are randomized to monthly visits will continue to have monthly visits until M9; the month 4, 5, 7, and 8 visits will be special issue counseling visits. We will discontinue all interventions by the month 9 study visit (participants will be exited from two-way SMS and WhatsApp, special issue counseling and drug-level feedback will not occur at the month 9 visit). The primary outcome for the combined intervention is the proportion with high adherence measured by

intracellular TFV-DP levels at 9 months. Drug levels will be measured retrospectively using DBS samples. We will utilize DBS TFV-DP levels to assess cumulative dosing in the prior month. A threshold of 500 fmol/punch for counseling participants. For the outcome, we will use a category of 700 fmol/punch to categorize participants as highly adherent as this was associated with high efficacy in open label use of PrEP among MSM. The threshold of TFV-DP levels and HIV incidence in women PrEP users has not been identified.¹⁶

The secondary adherence measurements will be TFV-DP concentrations at Month 2.

6.2. Endpoints

6.2.1.Primary Endpoint

The primary outcome is dried blood spot drug concentrations above 700 fmol/punch at 9 months.

6.2.2.Secondary Endpoints

- TFV-DP concentrations above 700 fmol/punch at 2 months.
- TFV-DP concentrations at 2 and 9 months as a continuous measurement
- Correlates of PrEP adherence at 2 and 9 months, adjusted for study arm.
 - Covariate characteristics assessed at baseline and follow-up will include: Sociodemographic characteristics; partnership characteristics; partner's HIV status; sexual behaviors; HIV risk perception; HIV stigma; PrEP interest; self-efficacy; alcohol and drug use; gender-based violence (GBV); disclosure to peers, family members, teachers, and partner(s) about PrEP use and participation in the study, and level of engagement with the different intervention approaches (e.g., number of SMS messages sent, number of WhatsApp messages sent, satisfaction with intervention received).
- Proportion of young women who discontinue PrEP, timing of discontinuation, and factors associated with PrEP discontinuation.
- Frequency of responding to SMS and WhatsApp messages over follow-up, stratified by “responder” or “non-responder” status after Month 3; content of WhatsApp discussions over follow-up, stratified by “responder” or “non-responder” status after Month
- Qualitative factors that influence women's decisions to use and adhere to PrEP, acceptability of PrEP in the first 2 months after PrEP acceptance, and satisfaction/preferences for the randomized intervention(s) received.
- Qualitative perceptions of our intervention package and opinions on scalability of the interventions from clinic staff and key informants' perspectives.

6.2.3.Exploratory endpoints

- Incident HIV infections, and adherence prior to HIV seroconversion based on drug levels
- Genotypic resistance among incident HIV infections
- Acceptability and feasibility of a urine point-of-care test for drug-level feedback counseling, among the subset of women who accept drug level feedback counseling via a new urine POC assay at their month 9 exit visit.

6.3. Accrual, Follow-up, and Sample Size

For the SMART trial design, the goal is to enroll and randomize up to 500 women in order to achieve an analysis sample size of approximately 350 women who return for their one-month study visit and will want to continue PrEP for a further 9 months: 175 per arm randomized into the first intervention at enrollment, continuing past their 1-month study visit and evaluable at 9 months. Up to 500 women who initiate PrEP will be enrolled over a period of approximately 18 months. 350 evaluable women

would have 96% power for the initial randomization to detect an increase from 40% response at 2 months to SOC + two-way SMS to 60% with the SOC + WhatsApp groups. Among the estimated 70-105 non-responders in each initial group, we have 79-96% power in each group of non-responders to detect a 30% difference in adherence at 9 months between women randomized to monthly counseling or drug level feedback. Pooling across the initial randomization, with 149-166 women we would have ~80% power to detect ~ 15-20% difference (Table 2).

Table 2: Power to assess differences in adherence by intervention strategies in each of the first and second stages using a one-sided $\alpha = 0.025$.

First Randomization			Second randomization (Pooled across first randomization)			
% Adherent				% Adherent		
WhatsApp + SOC N = 175	SMS + SOC N = 175	Power	Non-responders Total N	Monthly visits	Drug Level Counseling	Power
65%	40%	99%	166	40%	25%	84%
				50%	30%	89%
60%	40%	96%	175	40%	25%	86%
				50%	30%	91%
55%	40%	84%	184	40%	25%	88%
				50%	30%	91%

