1.2. Rationale

1.2.1. PrEP adherence support for young African women

Given persistently high HIV incidence rates (5-8%) among young women in sub-Saharan Africa, PrEP is an important prevention method that must be evaluated for its utility in young African women.

Randomized, placebo-controlled PrEP efficacy trials have demonstrated that adherence to PrEP is crucial for protection against HIV infection. Adherence levels have been lower among young persons, including young African women; PrEP adherence in the VOICE trial was negatively associated with age <25 years.² Among young women who enrolled in the VOICE and FEM-PRÉP trials, problems with product use included: failure to initiate PrEP use; difficulty with forming habits of daily pill-taking; and failure of sustained use in the face of other social, environmental, and cognitive demands.

There is a gap in how to deliver PrEP to young African women with a focus on maximizing adherence. The studies of PrEP among young South African women indicate that young women are motivated to use PrEP but there is substantial drop-off in the first few months and women may need additional adherence support when they have quarterly visits. First, in HPTN 067/ADAPT which randomized women to daily, time-driven intermittent or event-driven dosing of oral PrEP, half of the Cape Town participants were ≤25 years and adherence was highest in the daily dosing arm during the first few months of follow-up (92.5% of women at week 10, 79.3% at week 30 who had reported sex in the week prior had detectable tenofovir in plasma).²² Second, an open-label study (PlusPills) assessed PrEP acceptability, safety, and use among adolescents ages 15-19 in South Africa, enrolled 148 adolescents (99 women, 49 men). PrEP was well-tolerated, with no safety concerns. Adherence was reasonable (57% with detectable tenofovir in blood at 12 weeks) but decreased significantly when visit spacing increased from monthly to quarterly.²³

Available data from open-label PrEP demonstration projects among youth indicate that they may have greater adherence challenges with daily pill-taking than older persons, even in the context of known efficacy of PrEP. A study of 18-22 year old MSM in the US demonstrated that TFV-DP levels indicating ≥4 pills/week in the prior 3 weeks declined from 56% at week 4 to 34% at week 48, with a noticeable drop-off occurring

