4.2.1. Enrollment Visit

Women who agree to study participation will be consented for 9 months of follow-up. Women who are confirmed HIV- and not pregnant will be randomized to participate in one of two basic strategies for adherence support:

- Standard of care adherence counseling sessions and WhatsApp group participation
- Standard of care adherence counseling sessions and weekly two-way SMS communications

Randomization will be conducted with a ratio of 1:1 between the two study arms. Envelopes will be used to assign primary randomization.

Locator information will be collected and mobile phone numbers will be validated and texting and WhatsApp capacity assessed. Demographic and behavioral data will be collected, including information about HIV and pregnancy risk perception, depressive symptoms, trauma, stigma, HIV prevention, self-efficacy, self-esteem, sexual relationship power, transactional sex, intimate partner violence, alcohol and drug use, sexual behavior (number of partners, partner's HIV status, vaginal and anal sex with partners), and PrEP interest and readiness.

Clinical evaluations and procedures will include a contraception assessment, counseling and provision if desired, HIV pre and post-test counseling, risk reduction counseling and condom provision. Medical history including assessment for acute HIV and STI symptoms and concomitant medications will be conducted and a symptom-directed physical exam will be performed if indicated. Women who have symptoms potentially consistent with acute HIV infection (fever, rash, pharyngitis) will have enrollment deferred for at least 2 weeks at which time repeat serologic testing will be performed (and if positive will result in study exclusion). STI treatment will be administered per local standard of care. Blood, urine, and a self-administered vaginal swab will be collected.

HIV testing will be conducted according to national algorithm. Testing will be conducted for pregnancy, Hepatitis B serology (HepBsAg), serum creatinine for creatinine clearance, and diagnostic STI testing for trichomonas, gonorrhea, chlamydia and syphilis. Plasma and DBS will be stored.

One bottle of PrEP will be dispensed and women will be counseled per South African national guidelines, including about the importance of high PrEP adherence to achieve high levels of HIV protection, frequency, type and timing of side effects with oral FTC/TDF, and strategies for confidential storage and anticipating barriers to adherence.

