We estimate that we will need to enroll about 350 AGYW to detect an approximately 12% difference in PrEP adherence between the two-way SMS and WhatsApp groups (with brief standard of care counseling) at the nine-month study visit.

Data Analysis

Primary Analysis 1: Evaluate the effect of the mHealth interventions, in addition to regular clinic visits, on PrEP adherence at the nine-month study visit.

Analysis population: PrEP SMART participants enrolled and randomized to either the weekly two-way SMS arm or the WhatsApp groups.

- For an intent-to-treat analysis, we will include all randomized participants.
- For a modified intent-to-treat analysis, we will include only participants who attend at least one study visit between months 1-3.
- For a per protocol analysis, we will include all randomized participants who received full doses of the SMS and WhatsApp interventions as specified below.

Outcome: PrEP adherence at the nine-month study visit, defined as a binary outcome variable around TFV-DP levels of 700 fmol/punch

- We will also conduct secondary analyses with PrEP adherence measured as continuous TFV-DP levels and will provide descriptive summaries of PrEP adherence measured as a five-category variable: BLQ, BLQ-349 fmol/punch, 350-699 fmol/punch, 700-1249 fmol/punch, and ≥ 1250 fmol/punch.

Predictor(s) of interest: Randomized first-line intervention arm, either weekly two-way SMS or WhatsApp groups

Measures of intervention use for per protocol analysis:

- Completed SMS intervention: 1 = remained enrolled in the SMS intervention for the full follow-up period. 0 = opted out of the SMS intervention for at least 1 week of the follow-up period.
- Completed the WhatsApp intervention: 1 = remained enrolled in the WhatsApp intervention for the full follow-up period. 0 = opted out of the WhatsApp intervention for at least 1 week of the follow-up period.

Statistical analyses:

- 1) We will compute descriptive statistics to describe the full study population of all randomized individuals and to describe the study population in each of the six intervention groups.
- 2) We will compute descriptive statistics to describe the study population who were randomized and returned for at least one study visit between months 1-3 (the sample for the modified intent-to-treat analysis). We will also summarize reasons for discontinuing

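### The 96% first-stage power is for the month-2 tailoring response, not the month-9 primary comparison, and the SAP's 12-point figure for 350 women has no stated assumptions behind it

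*Protocol*

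**What the plan says.** **Power statement.** Protocol 6.3 plans up to 500 women randomized to reach about 350 for analysis, described as "175 per arm randomized into the first intervention at enrollment, continuing past their 1-month study visit and evaluable at 9 months". It states that these women "would have 96% power for the initial randomization to detect an increase from 40% response at 2 months"; the full contrast is "40% response at 2 months to SOC + two-way SMS to 60% with the SOC + WhatsApp groups". Table 2 repeats this contrast among its first-stage rows, at one-sided alpha 0.025.

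**What response means.** Protocol 3.1 (Table 1) and 4.2.4 define a responder by a month-2 TFV-DP of at least 500 fmol/punch together with no missed refill at month 1 or 2.

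**What the primary test is.** Protocol 6.2.1: "The primary outcome is dried blood spot drug concentrations above 700 fmol/punch at 9 months". Protocol 6.4.1 and SAP Primary Analysis 1 both make the first-stage comparison at the 9-month visit. The month-2 endpoint in Protocol 6.2.2 is secondary, and it too is cut at 700.

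**The SAP's sample size.** "We estimate that we will need to enroll about 350 AGYW to detect an approximately 12% difference in PrEP adherence" between the SMS and WhatsApp arms at nine months. No base rate, power, alpha or allowance for loss is given. SAP Study Design makes about 350 the number consented and randomized, roughly 175 per initial arm.

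**The concern.** The only first-stage power in the protocol is for a different time point, a different cut-off and a partly different construct (refills count) from the endpoint tested. Between month 2 and month 9, non-responders in both arms receive intensified support and adherence among responders may fall, so a 20-point gap in month-2 response need not persist to month 9. The SAP does address month 9, but its statement cannot be checked as it stands, and it uses 350 for a different quantity from the protocol.

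The risk lies in interpretation. A reader who takes 96% as the power of the WhatsApp-versus-SMS primary test could read a null result as good evidence of no difference. A reader of the SAP could believe that enrolling 350 is enough, where the protocol expects to need up to 500 to have 350.

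**Working it through.** **Inputs.** 175 evaluable per arm, 1:1, one-sided alpha 0.025 (Protocol 6.3 and Table 2; 4.2.1 for allocation). Month-2 response 60% vs 40% (Protocol 6.3). Month-9 rates exist only for re-randomized non-responders: 40% or 50% with monthly visits, 25% or 30% with drug-level counseling (Table 2). SAP: 350 randomized, 12 points.

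**Formula.** With difference d, mean rate m and n per arm: s0 = √[2m(1−m)/n], s1 = √[(p1(1−p1) + p2(1−p2))/n], power = Φ[(d − 1.96·s0)/s1].

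**Step 1: reproduce the 96%.** For 60% vs 40% and n = 175: s0 = 0.0535, s1 = 0.0524, (0.20 − 0.1048)/0.0524 = 1.82, power 96.6%. The stated figure is right for its inputs.

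**Step 2: confirm which rates these are.** If Table 2's first-stage rates are month-2 response, total non-responders should be 350 − 175 × (sum of the two rates).

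| First-stage rates | Computed | Table 2 |
|---|---|---|
| 65%, 40% | 166.25 | 166 |
| 60%, 40% | 175 | 175 |
| 55%, 40% | 183.75 | 184 |

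The match shows that the first-stage columns hold the responder rates feeding the second randomization.

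**Step 3: the SAP's 12 points.** For 40% vs 52% and n = 175: s0 = 0.0533, s1 = 0.0529, (0.12 − 0.1045)/0.0529 = 0.29, power 62%. Other base rates, with 350 evaluable and with 245 evaluable (350 × 0.70; the 30% is inferred from 1 − 350/500):

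| Base rate | Power, 350 evaluable | Power, 245 evaluable |
|---|---|---|
| 40% | 62% | 47% |
| 30% | 65% | 50% |
| 25% | 68% | 53% |
| 14% | 80% | 65% |

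Power is symmetric about 50%, so 74% vs 86% also gives 80%.

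**Step 4: detectable difference at 80% power, 175 evaluable per arm.** 14.9 points from a 40% base, 14.4 from 30%, 13.9 from 25%, 12.2 from 15%.

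**Step 5: illustration only.** Take 60% vs 40% response, and set non-responders to 32.5% at month 9 (the mean of 40% and 25%). Assume a share s of responders is above 700 at month 9, with s and the 32.5% equal in both arms. The arm rate is r·s + (1 − r)·0.325, so the gap is 0.20 × (s − 0.325).

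| s (assumed) | Month-9 rates | Gap | Power, n = 175 |
|---|---|---|---|
| 1.0 | 73.0% vs 59.5% | 13.5 points | 76% |
| 0.8 | 61.0% vs 51.5% | 9.5 points | 43% |
| 0.6 | 49.0% vs 43.5% | 5.5 points | 18% |

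Now let the first-stage effect continue, with assumed values of s = 0.75 vs 0.65 and non-responders 35% vs 30%. The rates are 0.6 × 0.75 + 0.4 × 0.35 = 59% and 0.4 × 0.65 + 0.6 × 0.30 = 44%: 15 points, 80% power.

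**The case against.** - **The 96% is not miscalculated, and the protocol names month 2 openly.** This stands. The defect is that the figure is the only first-stage power given and does not concern the endpoint tested.
- **A reader might infer that the 96% is power for the month-2 secondary endpoint.** The documents do not support that. The secondary endpoint is above 700 fmol/punch; response is at least 500 with no missed refill. The figure matches no listed endpoint, and labelling it as one would add a threshold error.
- **A reader might infer that the SAP's 12-point claim is wrong.** That goes too far. With no base rate, power or alpha stated, it can be neither reproduced nor refuted, and a low month-9 rate above 700 is possible: Protocol 1.2.1 reports that even detectable tenofovir fell below 50% between months 3 and 6 in a Cape Town cohort. The 40% base used here is itself a month-2 rate. What stands is that no rate in either sample-size section supports the claim at 80% power.
- **A reader might infer that the plan assumes no loss from month 1 to month 9.** The Protocol 6.3 wording combines continuing past month 1 with being evaluable at month 9, so the step from 500 to 350 can be read as covering loss through month 9. The SAP's sample-size text does not mention month-1 return at all.
- **A reader might take 18-76% as the trial's true power.** Those figures assume no first-stage effect after month 3, yet both mHealth interventions run to month 9, and a modest continuing effect restores about 80%. The cited fall, "declined from 56% at week 4 to 34% at week 48", comes from US MSM aged 18-22 and compares two prevalences; it does not measure persistence among responders.
- **Table 2's 55% vs 40% row already shows a 15-point contrast.** True, and it recomputes to 80.5% (stated 84%), but nothing labels it as a month-9 figure.

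**Conclusion.** The point holds as one about which quantity the power describes and about missing assumptions. The 96% is correct for the month-2 tailoring response and says nothing direct about the primary first-stage comparison, for which the protocol gives no rates or power. The SAP's 12 points with 350 women is unsupported: 62-68% power at base rates of 40% down to 25% with nobody lost, and 47-53% if the inferred 30% loss applies to 350 randomized. It would stand at 80% power with 350 evaluable and a base of about 14% or lower, or a correspondingly high one.

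These results rest on the protocol's one-sided 0.025, an unadjusted two-proportion comparison, and base rates that are assumptions at month 9. The loss figure is inferred, since neither document states a drop-out rate. Projections from month-2 response to month 9 are illustrative and depend heavily on whether the mHealth effect continues.

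**What to change.** 1. **Protocol 6.3 and Table 2:** label the 96% and the first-stage columns as power for the month-2 tailoring response (at least 500 fmol/punch and no missed refill), not for a listed endpoint.
2. **Protocol 6.3:** add month-9 power for the primary comparison. With 175 evaluable per arm at one-sided 0.025, power is 80% for about 14-15 points from a 25-40% base, and for about 12 points only from a base near 14-15%. State the month-9 rate assumed. If a projection from month-2 response is shown, give its persistence and continuing-effect assumptions and a range.
3. **SAP Sample size, Study Design and Study Size:** replace 350 enrolled with up to 500 randomized and about 350 evaluable at month 9, and give the base rate, power and alpha behind the detectable difference.

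The cost is wording in both documents and a less favourable stated power. Design, analysis and enrolment do not change.

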- 2) Primary analysis: We will use modified Poisson regression to assess the effect of the randomized second-line intervention on 9-month adherence by comparing TFV-DP levels across participants receiving monthly counseling versus participants receiving drug-level feedback, separately for (1) non-responders to the first-line SMS intervention and (2) non-responders to the first-line WhatsApp intervention. The effect of the randomized intervention will be estimated as a relative risk (RR) from the regression models, with study arm assigned at second randomization as the predictor of interest and robust standard error estimates.

Sensitivity analysis: If overall loss to follow-up in the full sample is $> 10\%$ by month 9 or if differential loss to follow-up between the two arms is $> 10\%$, we will repeat the primary analysis using inverse probability weights to adjust for the potential impact of censoring due to missing data.

Subgroup analysis: Subgroup-specific estimates of the intervention will be generated using the same models and analysis population as described in the primary analysis (above) but will also include subgroup indicator variable(s) and an interaction term between the subgroup indicator and second-line study arm in the model. Subgroups will be defined as follows:

- Age ≤ 20 years versus > 20 years
- 3) Secondary analyses:
 - We will also assess the effect of the intervention on the continuous PrEP adherence outcome using linear regression models to assess the difference in mean TFV-DP levels between those in the monthly problem-focused counseling group and those in the drug-level feedback group at month 9. If less than 40% of the sample has drug undetectable drug levels, we will assign those with undetectable drug levels a numeric drug level equal to half the limit of detection. If more than 40% of the sample has undetectable drug levels, we will reassess the value of this analysis.

- We will also consider evaluating the effect of second-line treatment stratified by reason for non-response; however, if the number of participants available for these stratified analyses is insufficient, we will not pursue these analyses.

Primary Analysis 3: Among the embedded dynamic treatment strategies, identify the optimal adherence support strategy in terms of PrEP adherence at the nine-month study visit, where additional adherence support is provided to those who have low adherence after the first two months of PrEP use.

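### The 79-96% power printed for the within-arm second-stage comparison has no stated rates or test, and at Table 2's drug-level rates it is about 72-77% to 88-91%

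*Protocol*

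**What the plan says.** Protocol 6.3 plans for 175 women per first-line arm, described as evaluable at 9 months. It then gives power for the second randomization inside each arm, claiming that "we have 79-96% power in each group of non-responders to detect a 30% difference in adherence at 9 months". The count behind this claim is 70 to 105 women per first-line arm. The sentence gives no adherence rates, no test and no alpha of its own.

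The next sentence turns to the combined comparison: "Pooling across the initial randomization, with 149-166 women we would have" about 80% power for differences of roughly 15 to 20 points. Table 2, at one-sided alpha 0.025, covers that pooled comparison with totals of 166, 175 and 184 non-responders. Its month-9 rates are 40% (monthly visits) v 25% (drug level) and 50% v 30%. No pair in it differs by 30 points.

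SAP Primary Analysis 2 makes the second-stage comparison "separately for (1) non-responders to the first-line SMS intervention and (2) non-responders to the first-line WhatsApp intervention". The SAP's sample size section addresses only the first-line comparison.

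**The concern.** The within-arm sentence is the only printed power for the test that SAP Primary Analysis 2 performs. It tells the reader that even the smaller stratum has close to 80% power for a 30-point difference. That cannot be checked without the rates, and the only month-9 rates the plan gives for the drug-level arm lead to lower figures at both ends.

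The counts also disagree within 6.3. The low end of 70 is 40% of 175, so it assumes 60% response. Table 2's first row has 65% response to WhatsApp, which leaves fewer women. The pooled 149-166 in the text differs from 166-184 in the table.

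If the smaller stratum is weaker than stated, a reader could take a null result there as better evidence of similarity between the two options than it is.

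**Working it through.** **Inputs.** One-sided alpha 0.025, critical value 1.96 (Table 2; assumed to apply to the sentence). 1:1 second randomization (Protocol 4.2.4). Difference d = 0.30. Non-responders per first-line arm:
- 175 × 0.40 = 70
- 175 × 0.60 = 105
- 175 × 0.35 = 61.25 (Table 2's 65% row; 61 + 105 = 166, the printed total)

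**Formulas.** With n per second-stage arm and p̄ the mean of p1 and p2, let s0 = √[2p̄(1−p̄)/n] and s1 = √{[p1(1−p1)+p2(1−p2)]/n}.
- Pooled-variance power = Φ[(d − 1.96·s0)/s1]
- Unpooled power = Φ[d/s1 − 1.96]

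**Reproducing 79-96%.** At 10% v 40%:
- Fisher's exact test (two-sided 0.05): 78.5% at 70 women, and 94.6% or 95.6% at 105, depending on which arm has 53.
- Pooled-variance formula: 78.8% at 61 women and 95.5% at 105. At the printed 70 it gives 84.1% (unpooled 87.1%).

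A continuity-corrected formula comes within 2 points of both ends at about 6-8% v 36-38%. By symmetry 60% v 90% gives the same power as 10% v 40%. With one fixed pair at 70 and 105, the pooled, unpooled and arcsine formulas do not reach both ends.

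**At Table 2's drug-level rates.** Worked case, 25% v 55%, n = 35: s0 = √(0.48/35) = 0.1171 and s1 = √(0.435/35) = 0.1115.
- Pooled: (0.30 − 0.2295)/0.1115 = 0.632, giving 73.6%
- Unpooled: 0.30/0.1115 − 1.96 = 0.731, giving 76.8%

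| Non-responders in the arm | 25% v 55%, pooled / unpooled | 30% v 60%, pooled / unpooled |
|---|---|---|
| 61.25 | 67.7% / 71.1% | 66.2% / 69.7% |
| 70 | 73.6% / 76.8% | 72.2% / 75.4% |
| 105 | 89.2% / 90.9% | 88.2% / 90.0% |

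At the printed counts the shortfall is 2 to 7 points at the low end (79% less 77% to 72%) and 5 to 8 at the high end (96% less 91% to 88%).

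**Sensitivity to a further 10% loss (not stated in the plan).** 0.9 × 61.25 = 55.1 women: 61-67%. 0.9 × 105 = 94.5 women: 85-88%.

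**Table 2, first randomization, 55% v 40%, 175 per arm.** s0 = √(0.49875/175) = 0.0534; s1 = √(0.4875/175) = 0.0528. Power is 80.5% pooled, 81.1% unpooled and 80.5% arcsine, against 84% printed. A continuity correction lowers it to 77.4% and one-sided 0.05 raises it to 88.1%, so neither explains 84%. The rows for 60% and 65% recompute to about 97% and over 99%, close to the printed 96% and 99%.

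**The case against.** The sentence states no rates, so any recomputation has to choose them. Table 2's pairs belong to the pooled comparison. Holding the drug-level arm at 25% or 30% moves monthly visits to 55% or 60%, which the plan nowhere gives for month 9. Holding monthly visits at Table 2's 40% instead gives 10% v 40%, and that roughly returns the printed range. This stands: a reader might infer that 79-96% is arithmetically impossible, and the documents do not support that. What they show is an undisclosed and favourable assumption. The 10% rate is less than half of Table 2's lowest drug-level rate, and Fisher's test is named nowhere in the plan. If Fisher's test were adopted, 25% v 55% and 30% v 60% would give only 66% and 62% at 70 women. Holding monthly visits at Table 2's 50% (20% v 50%) gives 76-79% at 70 and 91-92% at 105, which meets the low end at best.

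A reader might also infer a 10% loss, since 149-166 is close to 90% of 166-184 (149.4 and 165.6), and conclude that true power is 61-88%. The plan states no such loss and calls the 175 per arm evaluable at 9 months. Up to 500 are enrolled to reach 350. The lower figures are therefore a sensitivity case only.

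Finally, Protocol 6.4.1 also allows pooling across first-line arms when there is no interaction, so the within-arm figure is not the whole second-stage case in the protocol. It is the whole case in SAP Primary Analysis 2.

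**Conclusion.** The point holds as a matter of disclosure and restatement. The 79-96% cannot be verified as written, and it is missed at both ends at the only drug-level rates the plan gives: about 72-77% at 70 women and 88-91% at 105. On Table 2's own 65% row the smaller stratum has 61 women and about 66-71% power.

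These figures assume one-sided 0.025, 1:1 allocation, no loss beyond the stated evaluable numbers, and Table 2's drug-level rates with 30 points added. They depend on that choice of rates and do not prove a calculation error in the sentence. The 84% in Table 2 for 55% v 40% does not depend on such a choice: rates and sample size are printed, and the result is 80-81% by the pooled, unpooled and arcsine formulas.

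**What to change.** In Protocol 6.3:
- State the two month-9 rates and the test behind the within-arm power. If 10% v 40% was intended, say so and justify it against Table 2.
- Use one set of non-responder counts in text and table (61 to 105 per first-line arm), and reconcile the pooled 149-166 with 166-184.
- Restate within-arm power for a 30-point difference at drug-level rates of 25-30% as about 66-71% (61 women), 72-77% (70) and 88-91% (105).
- Show any further 10% loss only as a labelled sensitivity case: about 61-67% at 55 women and 85-88% at 94-95.
- Correct the first-randomization power for 55% v 40% at 175 per arm from 84% to 80-81%.

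In the SAP, add the restated figure to Primary Analysis 2.

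The cost is wording only, with no change to enrolment or procedures. The stated power becomes less favourable.
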